5.1.5 Safety Oversight Committee

Due to the novel design of this study and limitations imposed by the risk of contagion, the study will be monitored by a Safety Oversight Committee (SOC). The SOC will assist in the oversight of the study execution and ongoing assessment of safety and efficacy. Members will be chosen based on clinical expertise in the areas of infectious disease, pulmonary/critical care and immunotherapy (eg, rheumatology) or study outcome interpretation. The SOC will be composed of BMS personnel, site investigators and external experts. External members will constitute the majority of all voting members. The SOC will be provided with periodic data outputs and meet on a regular schedule (ie, bi-weekly) or ad hoc basis as needed. The first meeting of the SOC will review the SOC charter and decide on the frequency of SOC data review meetings before finalizing the SOC. In the case that review of subjects grouped by treatment is required to assess changes to study conduct, this will be performed by a group of external members in a closed session. Details of the membership, meeting schedule, purpose and data access is found in the SOC charter.

5.2 Number of Participants

One hundred and twenty nine (129) participants will be randomized.

5.3 End of Study Definition

The start of the study is defined as the first visit for the first participant screened. End of study is defined as last visit or scheduled procedure shown in [Section 2](#) (Schedule of Activities) for the last participant. Study completion is defined as the final date on which data for the primary endpoint was or is expected to be collected, if this is not the same.

5.4 Scientific Rationale for Study Design

The goal of this Phase 2 study is to establish evidence for the efficacy and safety of the use of abatacept IV to prevent participants hospitalized with COVID-19, with respiratory compromise and evidence of immune activation, from progressing in severity. To do so, we have chosen to execute a blinded, placebo controlled, randomized study design. The main safety concern is the

possibility of a negative impact on viral clearance with clinical impact or an increase in the risk of secondary bacterial infection. Because of the unprecedented level of infectious risk in the general population, including hospital staff, usual study procedures and monitoring are not feasible.³⁵ The study has to be streamlined for ease and speed of execution. While a lot has been reported to infer the clinical course for COVID-19 patients, there are still many unknowns including the efficacy of all currently used disease specific effective therapies. Interpretation of open-label treatment experience in the setting of an ongoing potentially lethal pandemic is fraught with challenges.³⁶ The potential differential patient care and use of concomitant medication in an open-label setting will be confounded with the treatment effect. Only a blinded, randomized study can reliably provide information for interpretation but this presents other complex bioethical concerns and challenges. In a blinded study the impact on clinical decision for off-label use of other available immunotherapies would be the same in both treatment arms. This study design will partly mitigate the above concerns by adopting a randomization ratio favoring active treatment (ie, 2:1), allowing background therapy, utilizing a safety oversight committee to assess safety, and a sample size with robust power but with a higher level of significance in order to increase the speed to a larger, definite study if a positive signal is detected.

5.5 Justification for Dose

Abatacept is available in 2 formulations, lyophilized for intravenous infusion and pre-filled syringe for subcutaneous injection. Pharmacokinetic evaluation over 2 decades of clinical development has shown that the most relevant PK parameter are trough (C_{min}) levels which are best at predicting maximal efficacy and are driven by weight based dosing. Superior efficacy is observed with 10 mg/kg dosing in RA patients. Dosing frequency of Day 1, 15, 28 and every 28 days afterwards was established as an efficacious dosing regimen for reaching target C_{min} levels.

Evidence based on pharmacokinetic, pharmacodynamic and clinical efficacy data suggest that higher doses of abatacept would not be more effective in RA patients. Higher doses of abatacept at 30 mg/kg have been tested in BMS sponsored trials. In patients with PsA, higher doses did not produce better efficacy but did not result in any increase in safety signal. In inflammatory bowel disease, no clinical efficacy was seen. In lupus nephritis, higher doses were thought needed due to urinary losses of abatacept due to the severe proteinuria unique to this disease. None of these studies suggested higher abatacept doses were associated with increased safety concerns.

More frequent dosing and higher doses of abatacept have been used empirically in many settings. While BMS is aware that this happens on occasion in the clinical practice for the care of RA patients, it happens most notably in the off-label treatment of other disease states. Children with active, refractory systemic onset JIA have been treated with empirical doses of up to 18 mg/kg every 3 weeks.³⁷ Common variable immunodeficiency (CVID) is a group of genetically defined conditions characterized by immune dysregulation and immunodeficiency, many of which are characterized by CTLA-4 deficiency or impaired expression.³⁸ Successful treatment with abatacept has been reported extensively with infusion as high as 20 mg/kg every 2 weeks.^{39,40} Immune checkpoint inhibitor associated myocarditis is a rapidly progressive adverse event with

high morbidity and mortality. Abatacept has been used successfully to reverse this process in refractory cases using weekly IV doses of 500 mg or higher.¹⁷

The largest experience with alternative abatacept dosing regimens comes from the study of acute graft-versus-host disease (aGVHD) prevention investigator initiated program.^{19,20} In this setting, abatacept was given at 10 mg/kg on days -1, +5, +14, and +28. Preliminary PK analysis shows C_{min}s above 40 mg/mL, which is well above the C_{min} known to show optimal efficacy for RA patients.⁴¹

There is not enough information available to suggest that an alternative to the approved IV dose is required in the setting of COVID-19 but there is empirical evidence that higher doses (either on a per weight basis or frequency) may be beneficial and not carry untoward risk. Given the nature of the clinical course, it is likely that a single abatacept dose of 10 mg/kg will be sufficient for clinical effect since supratherapeutic drug levels will be achieved for all study participants for at least 3 weeks.

6 STUDY POPULATION

For entry into the study, the following criteria **MUST** be met.

6.1 Inclusion Criteria

1) Signed Written Informed Consent

- a) Participant is willing to participate in the study and has signed the Informed Consent Form (ICF).

2) Type of Participant and Target Disease Characteristics

- a) Adults with a confirmed virological diagnosis of SARS-CoV-2 infection (by RT-PCR). Any positive test, at either the time of or prior to hospitalization, is suitable. Results must be documented.
- b) Hospitalized (or in the Emergency Department awaiting a bed after hospitalization)
- c) Respiratory compromise as defined by requirement of oxygen supplementation to maintain oxygen saturation $\geq 93\%$ but not requiring mechanical ventilation.
- d) Abnormal chest image (ie, chest X-ray, computerized tomography [CT] or high-resolution CT [HRCT]) consistent with COVID-19 and no evidence of any other serious medical condition that would serve as an exclusionary criterion.

3) Age and Reproductive Status

Investigators shall counsel women of childbearing potential (WOCBP) participants, and male participants who are sexually active with WOCBP, on the importance of pregnancy prevention and the implications of an unexpected pregnancy.

- The investigator shall evaluate the effectiveness of the contraceptive method in relationship to the first dose of study intervention.
- Local laws and regulations may require the use of alternative and/or additional contraception methods.

- a) Female Participants
 - i) Females, ages ≥ 18 years or local age of majority
 - ii) Women who are not of childbearing potential are exempt from contraceptive requirements
 - iii) Women participants must have documented proof that they are not of childbearing potential.
 - iv) WOCBP must have a negative highly sensitive urine/serum pregnancy test (minimum sensitivity 25 IU/L or equivalent units of HCG) performed during screening prior to the start of study treatment.
 - (1) If a urine test cannot be confirmed as negative (eg, an ambiguous result), a serum pregnancy test is required. In such cases, the participant must be excluded from participation if the serum pregnancy result is positive
 - v) The investigator is responsible for review of medical history, menstrual history, and recent sexual activity to decrease the risk for inclusion of a woman with an early undetected pregnancy
 - vi) WOCBP must agree to follow instructions for method(s) of contraception defined in [Appendix 4](#) and as described below and included in the ICF.
 - vii) WOCBP are permitted to use hormonal contraception methods (as described in [Appendix 4](#))
 - viii) A female participant is eligible to participate if she is not pregnant or breastfeeding, and at least one of the following conditions applies:
 - (1) Is not a WOCBP
 - OR
 - (2) Is a WOCBP and using a contraceptive method that is highly effective (with a failure rate of $<1\%$ per year), preferably with low user dependency, as described in [Appendix 4](#) during the intervention period and for at least 70 days and agrees not to donate eggs (ova, oocytes) for the purpose of reproduction for the same time period
- b) Male Participants
 - i) Males, ages ≥ 18 years or local age of majority
 - ii) Males who are sexually active with WOCBP must agree to follow instructions for method(s) of contraception defined in [Appendix 4](#) and as described below.
 - iii) Azoospermic males are exempt from contraceptive requirements.
 - iv) No additional contraceptive measures are required to be used

6.2 Exclusion Criteria

1) Medical Conditions

- a) Woman who are breastfeeding
- b) Participants with confirmed, clinically serious acute infection in the previous 30 days:
 - i) Confirmed is defined as culture positive or established by any other lab-based diagnostic testing or imaging.

- ii) Clinically serious is defined as infection involving deep tissues or organs (eg, cellulitis, upper urinary tract, lower respiratory tract).
- iii) Exclusion of a highly suspected serious infection (ie, not yet confirmed) is at the discretion of the investigator.
- c) Participants with history of chronic or recurrent bacterial infection (eg, chronic pyelonephritis, osteomyelitis, bronchiectasis).
- d) Medical history of known or suspected active or latent tuberculosis (TB), active hepatitis B, hepatitis C or HIV infection.
- e) TB risk will be further ascertained by review of history and most recent CXR.
- f) Hepatitis B virus (HBV) testing will be ordered (surface antigen and core antibody). If either is positive, reflex testing for HBV DNA by PCR will be obtained.
- g) Hepatitis C virus (HCV) testing will be ordered (HCV antibody). If positive, reflex testing for HCV RNA by PCR will be obtained.
- h) Current clinical findings of severe, progressive, or uncontrolled renal, hepatic, hematological, gastrointestinal, pulmonary, psychiatric, cardiac, endocrine, neurological, or cerebral disease, including severe and uncontrolled infections, such as sepsis and opportunistic infections (except COVID-19). Caution should be used when randomizing participants with severe COPD or frequent COPD exacerbations. Concomitant medical conditions that, in the opinion of the Investigator, might place the participant at unacceptable risk for participation in this study.
- i) Participants who have received any live vaccines within 3 months of the study drug administration or are scheduled to receive live vaccines during the study. Participants who are in close contact with others who have received a live vaccine may be enrolled at the Investigator's discretion.
- j) Participants with a history of (within 12 months of signing the ICF), or known current problems with drug or alcohol abuse history or known cirrhosis, including alcoholic cirrhosis.
- k) Participants who are impaired, incapacitated, or incapable of completing study related assessments.

2) Prior/Concomitant Therapy

- a) Participants who have been exposed within 1 month or five half-lives, whichever is longer, to any treatment with an approved or investigational targeted immunotherapy including, but not limited to, infliximab, etanercept, anakinra, rituximab, tocilizumab, golimumab, certolizumab, sirolumab, tofacitinib, baricitinib, upadacitinib, or filgotinib.
- b) Systemic corticosteroid within 2 weeks of randomization at doses above prednisone 10 mg, or other equivalent.
- c) Prior exposure to BMS-188667 (abatacept).

3) Physical and Laboratory Test Findings

- a) Hemoglobin (Hgb) < 8.5 g/dL.
- b) White Blood Count (WBC) < 3,000/mm³ ($3 \times 10^9/L$).
- c) Platelets < 75,000/mm³ ($100 \times 10^9/L$).

- d) Serum creatinine $> 2 \times$ ULN.
- e) Serum alanine aminotransferase (ALT) or aspartate aminotransferase (AST) $> 5 \times$ ULN.
- f) Any test results that, in the opinion of the Investigator, might place the participants at unacceptable risk for participation in this study.

4) Allergies and Adverse Drug Reaction

- a) Hypersensitivity to the IP and/or its excipients

5) Other Exclusion Criteria

- a) Prisoners or participants who are involuntarily incarcerated. (Note: under certain specific circumstances and only in countries where local regulations permit, a person who has been imprisoned may be included or permitted to continue as a participant. Strict conditions apply and Bristol-Myers Squibb approval is required.
- b) Participants who are compulsorily detained for treatment of either a psychiatric or physical (eg, infectious disease) illness.

Eligibility criteria for this study have been carefully considered to ensure the safety of the study participants and that the results of the study can be used. It is imperative that participants fully meet all eligibility criteria.

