Participants who complete the 28 day Double-blind Treatment Period will be monitored for study endpoints and will have follow-up information captured for Days 35, 42, 49 and 60, to perform safety and clinical status assessments. If routine safety labs are performed in this period, they should also be captured in the study record. Medical care in this period will also follow local standards and there will be no restrictions on treatment choices.

Post-hospitalization

Participants who are discharged from hospital care at any point before the end of this 60-day period will have remote follow-up visits. Post-hospital care is not considered part of this trial but outcomes up to 60 days are of interest. Participants who are discharged, whether home or to any form of assisted care facility, will be contacted remotely by the study team (eg phone, e-mail) to ascertain clinical status, weekly until Day 60. As a rule, remote contact should be performed approximately every 7 days. If the participants is discharged prior to Day 28, one of the remote contacts should be on Day 28 (± 2 days) to coincide with the study primary endpoint. If discharge occurs after Day 28, remote contacts should occur as close as possible to study Days 35, 42, 49, and 60, at approximately 7 day intervals. Level of activity (ie ambulatory status), oxygen requirement (eg home oxygen therapy), current location (eg home) and any intercurrent adverse event (eg infection) will be assessed and added to the study record.

Number of Participants: 129 randomized participants in a 2:1 ratio (abatacept: placebo), both on standard of care.

Treatment Arms and Duration:

There will be 2 treatment arms, abatacept plus standard of care versus placebo plus standard of care. Both arms will last for 60 days with a primary endpoint at Day 28.

Study treatment:

Abatacept 10 mg/kg IV, reconstitutes in 100 mL of an appropriate diluent and administered over 30 minutes. The minimum total dose will be 500 mg and the maximum total dose will be 1000 mg.

Table 1-2: Study Treatment for Study IM101873

Medication	Potency	IP/Non-IP
Abatacept	250 mg/vial	IP

Abbreviations: IP = investigational product; mg = milligram; IV= intravenous.
Note: BMS will provide Abatacept to all investigating sites.

Safety Oversight Committee:

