7.1 Treatments Administered

The selection and timing of dose for each participant is as follows:

Table 7.1-1: Selection and Timing of Dose

Study Treatment	Unit dose strength(s)/Dosage level(s)	Dosage formulation Frequency of Administration	Route of Administration
Abatacept	10 mg/kg	Day 1	IV
Placebo	Normal saline or 5% Dextrose in water ^a	Day 1	IV

Abbreviations: IV = intravenous; kg = kilogram; mg = milligram

^a Normal Saline or 5% Dextrose in water will be provided by the investigational site

Each investigator will be responsible for supplying any intravenous administrative solutions [Sterile Water for Injection (SWFI), 5% Dextrose in Water Injection (D5W), 0.9% Sodium Chloride Injection (NS)] needed for the reconstitution and dilution of investigational product identified in the protocol. D5W and NS will act as the intravenous placebo for this study. Handling and dispensing instructions will be provided separately to the unblinded pharmacist.

The dose of abatacept will be 10 mg/kg with a maximum dose of 1000 mg. Study medication will be administered in a fixed volume of 100 mL at a constant infusion rate over approximately 30 minutes. The IV line must be flushed with 25 mL of D5W or NS solution at the end of the infusion.

The administration window will be within 24 hours of randomization.

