9 STUDY ASSESSMENTS AND PROCEDURES

- Study procedures and timing are summarized in the Schedule of Activities.
- Protocol waivers or exemptions are not allowed.
- All immediate safety concerns must be discussed with the Sponsor immediately upon occurrence or awareness to determine if the participant should continue or discontinue treatment.

- Adherence to the study design requirements, including those specified in the Schedule of Activities, is essential and required for study conduct.
- All screening evaluations must be completed and reviewed to confirm that potential participants meet all eligibility criteria before randomization. The investigator will maintain a screening log to record details of all participants screened and to confirm eligibility or record reasons for screening failure, as applicable.
- Procedures conducted as part of the participant's routine clinical management (eg, blood count) and obtained before signing of informed consent may be utilized for screening or baseline purposes provided the procedure meets the protocol-defined criteria and has been performed within the timeframe defined in the Schedule of Activities.

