9.4.6 Clinical Safety Laboratory Assessments

- Investigators must document their review of each laboratory safety report.

A local laboratory will perform the analyses and will provide reference ranges for these tests. All lab results will be available in an unblinded fashion to hospital clinical staff caring for the participant.

The study will rely on routine safety labs performed as part of routine hospital care. When available, the hematology and chemistry labs listed below will be included in the study record.

Screening for active viral hepatitis B or C is routine in abatacept studies and will be performed in this study, although in a different fashion. Hepatitis B reactivation has been seen in patients treated with abatacept but only in the setting of continuous use, and is a labeled warning. Reactivation of hepatitis C is not a labeled warning. Speed of screening and treatment precludes the feasibility of completing assessment during the screening period and are not warranted. Screening antibodies test will be performed but results will not be needed prior to randomization. If positive results are

noted, confirmatory nucleic acid reflex testing should be ordered and if positive monitor as appropriate.

Table 9.4.6-1: Clinical Safety Laboratory Assessments

Hematology	
Hemoglobin	
Hematocrit	
Total leukocyte count, including differential	
Platelet count	
Chemistry	
Aspartate aminotransferase (AST)	Sodium
Alanine aminotransferase (ALT)	Potassium
Total bilirubin	Chloride
Direct bilirubin	Calcium
Alkaline phosphatase	Phosphorus
Creatinine	Creatinine kinase
Blood urea nitrogen (BUN)	
Uric acid	
Glucose	
Total protein	
Albumin	
Serology	
Hepatitis B surface antigen, hepatitis B core antibody. If either are positive, reflex to hepatitis B DNA testing	
Hepatitis C antibody. If positive reflex to HCV RNA testing	
Other Analyses	
Pregnancy test (WOCBP only: screening)	

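### Exclusion criterion 3c prints two unequal platelet limits: 75,000/mm³ is 75 x 10^9/L, not 100 x 10^9/L

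*Protocol*

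**What the plan says.** Protocol Section 6.2, under physical and laboratory test findings, lists the haematology exclusions. Criterion 3c reads "Platelets < 75,000/mm³ ($100 \times 10^9/L". Criterion 3b, immediately above, has the same layout: "White Blood Count (WBC) < 3,000/mm³ ($3 \times 10^9/L". In both lines a conventional-unit limit is followed by a figure per litre in parentheses.

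The protocol is strict about applying these limits. Section 6.2 closes with "It is imperative that participants fully meet all eligibility criteria", and Section 9 adds "Protocol waivers or exemptions are not allowed". Section 9.4.6 leaves testing to the sites: "A local laboratory will perform the analyses and will provide reference ranges for these tests".

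A smaller mismatch sits in the dosing text. The Synopsis says "The minimum total dose will be 500 mg and the maximum total dose will be 1000 mg", while Section 7.1 says only "The dose of abatacept will be 10 mg/kg with a maximum dose of 1000 mg". Table 7.1-1 gives 10 mg/kg with neither limit.

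**The concern.** A parenthesis in this position is normally the same limit in other units. In 3c it is not, so the criterion contains two different cut-offs. A site whose laboratory reports per mm³ would exclude below 75,000. A site whose laboratory reports in 10^9/L could take the only figure given in its own units and exclude below 100.

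The same patient could then be randomized at one site and screen-failed at another. The protocol leaves little room to sort this out case by case. Screening and randomization must be finished within 48 hours of consent (Section 5.1.1), and rescreening is ruled out (Section 6.4.1). A participant enrolled at, say, 85 x 10^9/L could also be recorded as an eligibility deviation by a monitor who reads the other figure.

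The Amendment 02 rationale shows that sites in this trial have read an exclusion literally, to the detriment of recruitment: criterion 1b was rewritten for that reason. Criterion 3c is not among the changes listed.

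**Working it through.** **Inputs** (all from Protocol Section 6.2 unless stated)

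- Platelet limit, conventional units: 75,000/mm³ (3c)
- Platelet limit, parenthesis: 100 x 10^9/L (3c)
- White-cell limit: 3,000/mm³, parenthesis 3 x 10^9/L (3b)
- Planned number randomized: 129 (Section 5.2)

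**Formula.** 1 L = 10^6 mm³, so count per litre = count per mm³ x 10^6.

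**Step 1: check the method on the neighbouring line.** White cells: 3,000 x 10^6 = 3 x 10^9/L. This reproduces the protocol's figure, so the parenthesis is meant as a unit conversion.

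**Step 2: apply it to platelets.** 75,000 x 10^6 = 75 x 10^9/L. The protocol prints 100 x 10^9/L, so its figure is not reproduced.

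**Step 3: convert the parenthesis back.** 100 x 10^9 / 10^6 = 100,000/mm³.

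**Step 4: size of the gap.** 100 / 75 = 1.33. The disputed band runs from 75 up to, but not including, 100 x 10^9/L, a width of 100 - 75 = 25 x 10^9/L.

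| Platelets (10^9/L) | Limit 75,000/mm³ | Limit 100 x 10^9/L |
|---|---|---|
| below 75 | excluded | excluded |
| 75 to below 100 | eligible | excluded |
| 100 or more | eligible | eligible |

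**Step 5: how many places could be involved.** The protocol gives no platelet distribution, so this is an assumption. Suppose 1% to 5% of otherwise eligible candidates lie in the band:

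- 0.01 x 129 = 1.3
- 0.05 x 129 = 6.45

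That is about 1 to 6 of the 129 places. If every site used the lower limit, these places would go to people in the band; if every site used the higher limit, they would go to others. With mixed practice the number falls in between.

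**Step 6: look for a resolution elsewhere.** No other section states a platelet eligibility limit. Neither change summary, as far as it is legible, mentions 3c. Criterion 3f lets the investigator exclude on any worrying result but does not say which limit applies.

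**Dose wording (editorial).** 10 mg/kg x 50 kg = 500 mg, so the Synopsis minimum matters only below 50 kg. At 40 kg, 10 x 40 = 400 mg under Section 7.1, against 500 mg under the Synopsis.

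**The case against.** The strongest reply is that the two figures do not have equal standing. The criterion has one inequality sign, attached to 75,000/mm³, and criterion 3b shows that the parenthesis is only a restatement. On an ordinary reading the limit is 75,000/mm³ with a faulty conversion. That is the likelier intention, and it is why the lower figure comes first in the fix. It does not remove the risk for a reader working in 10^9/L, and the protocol does not confirm the intention.

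Second, Section 9.4.6 says that local laboratories run the tests; it does not say that any of them report in 10^9/L. This is fair: divergent handling between sites is a possibility, not something the protocol documents.

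Third, the 1% to 5% share has no source, and a wrongly screen-failed candidate is simply replaced, because enrolment continues to target. This also stands. The estimate is illustrative, and the firm result is the 25 x 10^9/L band.

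Fourth, no safety harm is shown. The drug risks identified in Section 3.2.2 are infections and infusion reactions, and nothing in the protocol links the platelet cut-off to a risk of abatacept. That limits the weight of the point without making the criterion correct.

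Finally, the dose wording is a separate omission, not a conflicting minimum. Material outside the protocol may already settle it: "Handling and dispensing instructions will be provided separately to the unblinded pharmacist". It is included only because it can be tidied in the same edit, and the platelet point does not depend on it.

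**Conclusion.** The error is certain: the conversion in criterion 3c is wrong, in current text, in an operative eligibility criterion. The higher figure exceeds the lower by a factor of 1.33, and patients with platelets from 75 to below 100 x 10^9/L get opposite answers. How many patients that is cannot be derived from the protocol; 1 to 6 of 129 rests entirely on the assumed 1% to 5%.

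The consequence is confined to who enters the trial and how eligibility deviations are recorded. Because the criterion acts before randomization, it does not bias the treatment comparison or alter the one-sided 0.15 level, the power or the sample size. It should be fixed because it governs eligibility and the correction costs almost nothing. Which limit was intended is for the sponsor to confirm.

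The dose wording is editorial. It affects only participants under 50 kg, and Section 5.5 reports no added safety concern at higher abatacept doses.

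**What to change.** State one platelet limit in matching units. The natural correction keeps the figure that carries the inequality: below 75,000/mm³ (75 x 10^9/L). If the clinical team confirms that the higher limit was intended, write below 100,000/mm³ (100 x 10^9/L).

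In the same edit, either carry the 500 mg minimum dose into Section 7.1 and Table 7.1-1 or remove it from the Synopsis, and check that the pharmacist's instructions agree.

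The cost is a one-line correction by amendment or administrative letter; Appendix 2 already provides for revision by letter, with the ethics committees informed. No analysis, sample size or data collection changes.
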